## Clinical Investigation Plan (CIP)

### 1.3 Overall synopsis of the clinical investigation

Background and Rationale	
████████ claims the █████ 3D ear scanning solution to streamline clinical processes. According to █████, with the █████, you can:
 
 
• save time and money on handling earmolds and hearing aids
 
• secure digital patient records for easy storage, retrieval and use
 
• ensure a better fit and reduce remakes and returns,
 
• enjoy a cleaner procedure
 
 
████████ ████████ ████████
																	
	
Previous research has been done at Sonova HQ to analyze the quality of █████ ear scans compared to traditional earmold impressions. However, to fully understand the value drivers, further data is needed exploring efficiency and preferences in comparison to traditional EMI methods. In addition, the department of Audiological Care is interested in finding out if this is a viable piece of equipment for their clinics. The results of previous research regarding quality of the █████ has warranted a further look into efficiency and subjective preference.
																	
Investigation Objectives	
The primary objective of this study is to identify any significant differences in the time required for a clinician to complete the workflow of an █████ impression compared to traditional earmold impressions.
 
The secondary objective of this study is to identify any significant preference for both the HCPs and patients when comparing the █████ to traditional EMI procedures.
																	
Outcome(s) / Endpoints:	
Time (mm:ss) will be recorded to quantify the duration of each impression procedure.
 
Questionnaires will be administered to assess overall preferences of both the researchers and subjects.
																	
Investigation Design	
 Interventional Study
 
  
 Investigation Model Masking	Allocation	
   
  Single Group	 single-blinded	 N/A (for single-)	
 
  Parallel	 double-blinded	 Randomized	
 
  Crossover	 no masking	 Nonrandomized	
 
  Factorial	 other:		
 
  Sequential			
  
	Investigation Model Masking	Allocation	 Single Group	 single-blinded	 N/A (for single-)	 Parallel	 double-blinded	 Randomized	 Crossover	 no masking	 Nonrandomized	 Factorial	 other:		 Sequential		
Investigation Model Masking	Allocation																	
 Single Group	 single-blinded	 N/A (for single-)																
 Parallel	 double-blinded	 Randomized																
 Crossover	 no masking	 Nonrandomized																
 Factorial	 other:																	
 Sequential																		

## Clinical Investigation Plan (CIP)

	Number of Arms: [2]		
	 Observational Study		
	Investigation Model		Time Perspective
	 Cohort	 Ecologic	 Retrospective
	 Case-Control	 Family-based	 Prospective
	 Case-only	 other:	 Cross-sectional
	 Case-crossover		 other:
	Number of Groups/ Cohorts: [1]		
Type of design	 Exploratory	 Confirmatory	 Observational
Inclusion / Exclusion criteria:	External auditory canal must be present and medically unremarkable to facilitate impressions. Participants with surgical ears or without external auditory canals must be excluded.		
Measurements and procedures:	Three researchers will be facilitating these appointments to limit variability of researcher skill across the two conditions. Researchers will familiarize themselves with the [REDACTED] equipment through independent practice prior to a training facilitated by [REDACTED] (occurring April 22nd) and will follow [REDACTED] training recommendations (perform scans on 10+ ears following in-person training) prior to data collection. Participants will be seen for one appointment. The researcher will perform both traditional earmold impressions and 3D ear scans on both ears (conditions will be randomized and counterbalanced across participants). An additional researcher will use a stop watch to quantify the time (mm:ss) it takes for each condition, for both ears. At the end of the appointment, participants will also be asked to complete a subjective questionnaire regarding each condition, focusing on their perception of comfort and level of involvement throughout the impression taking. The resulting data will be compiled for all participants and analyzed using a T-test, to identify any significant differences in the time it takes to complete each method of earmold impressions, in addition to any differences in subjective domains.		
Intervention:	[REDACTED] 3D Ear Scanning Solution		
Control Intervention (if applicable):	Traditional silicone earmold impression material, administered by a cartridge impression gun.		
Number of Participants with Rationale:	N = 30 (10 participants per researcher). Both conditions will be measured for each participant. This sample population will provide an adequately powered study under the assumption that time variance of each condition is within approximately 5 minutes.		

SRF-371

Confidential and proprietary.

This document and its contents are confidential and proprietary to Sonova and shall not be reproduced or otherwise disclosed to anyone other than Sonova employees without written authorization from Sonova.

This printout is an uncontrolled copy. The original is stored in the Document Management System  
Template: TPL-368 [2]

## Clinical Investigation Plan (CIP)

Investigation Duration:	Approximately 1 month	
Investigation Schedule:	Month/ Year of First-Participant-In (planned): MAY/2021 Month/ Year of Last-Participant-Out (planned): JUN/2021	
Statistical Considerations:	Analysis of procedure time data will take place at the conclusion of the trial. The intended analysis assumes a normally-distributed response variable. As such, procedure times for each methodology will be tested for normality using a Shapiro-Wilk test	
Trial registration:	U.S. National Library of Medicine – clinicaltrials.gov ClinicalTrials.gov Identifier: NCT05000047	
Investigation category and Rationale	Non-significant Risk Investigation	
US FDA regulated Device (applicable in the US)	 Yes  No	
US FDA IDE (applicable in the US)	 Yes  No	, IDE Number: [xxx]
Clinical Phase:	 Pre-market [Exploration/ Confirmation]	 Post-Market [Confirmation/ Observational]
Good Clinical Practice (GCP) Statement:	This investigation will be conducted in compliance with the protocol, the current version of the Declaration of Helsinki, ISO 14155 (as far as applicable) as well as all national legal and regulatory requirements.	

## 2 Identification and description of the investigational device

### 2.1 Description of the investigational device and its intended purpose.

SRF-371

Confidential and proprietary.

This document and its contents are confidential and proprietary to Sonova and shall not be reproduced or otherwise disclosed to anyone other than Sonova employees without written authorization from Sonova.

This printout is an uncontrolled copy. The original is stored in the Document Management System  
 Template: TPL-368 [2]

## Clinical Investigation Plan (CIP)

The [REDACTED] is an alternative approach to traditional impression procedures. By creating a 3D digital scan, [REDACTED] claims that the [REDACTED] has potential to reduce shipping and procedural times in a cost effective manner.

## 2.2 Legal manufacturer of the investigational device.

## 2.3 Model/type, including software version and accessories

3D Ear Scanner

SN: [REDACTED]

## 2.4 Traceability during and after the clinical investigation

Participants will be assigned a non-identifying subject identification number. This number will be used to trace scans and impressions and will correspond to the respective participant.

## 2.5 Intended purpose of the investigational device in the proposed clinical investigation.

The [REDACTED] is an alternative approach to traditional impression procedures. By creating a 3D digital scan, [REDACTED] claims that the [REDACTED] has potential to reduce shipping times and procedural times in a cost effective manner. (See section 2.1)

## 2.6 Populations and Clinical indications

External auditory canals must be present and medically unremarkable to facilitate impressions. Participants with surgical ears or without external auditory canals must be excluded.

## 2.7 Description of the materials used

████████ 3D Ear Scanner- The █████ is an alternative approach to traditional impression procedures. By creating a 3D digital scan, █████ claims that the █████ has potential to reduce shipping times and procedural times in a cost effective manner. (See section 2.1)

## Traditional silicone earmold impression material- Dreve Otoform A/flex

- Shore Rating = 25 +/- 2 Shore A

\*Used with 48ML Impression Gun

## 2.8 Summary of the necessary training and experience

Researchers will familiarize themselves with the [REDACTED] equipment through independent practice prior to a training facilitated by [REDACTED] (occurring April 22nd) and will follow [REDACTED]

## Clinical Investigation Plan (CIP)

training recommendations (perform scans on 20+ ears following in-person training) prior to data collection

### 2.9 Description of the specific medical procedures involved in the use of the investigational device.

The [REDACTED] 3D ear scanner is used to create a 3D mapping of the ear canal. This digital file is then used to produce an earmold. Traditional earmold impressions require an audiologist or HCP to place a dam to prevent impression material leakage, then fill the external auditory canal with silicone impression material. This material then has to set prior to being removed from the ear canal and then proceeds to production stages.

## 3 Justification for the design of the clinical investigation

### 3.1 Preclinical Evidence

N/A – The [REDACTED] 3D ear scanner is a post market device.

### 3.2 Clinical Evidence to date

Previous research has shown comparable quality of impression between [REDACTED] 3D ear scanner and traditional earmold impression procedures. However, it is unknown how [REDACTED] claims of increased efficiency applies to the workflow of Sonova's retail facilities. In particular, Audiological Care has the need for supportive data in deciding whether or not the [REDACTED] 3D ear scanner adds value to their businesses. These value drivers of interest include procedural time, and subjective comfort and overall preference for patients and providers.

### 3.3 Description of clinical development stages

Post Market – Observational

- Registry
- Post Market Clinical Investigation

## 4 Risks and benefits of the investigational device and clinical investigation

### 4.1 Anticipated clinical benefits

Better understanding of the value drivers behind [REDACTED] 3D Ear Scanners. This data will support the decision making process for incorporating these products into Audiological Care clinics.

### 4.2 Anticipated adverse device effects

The devices used in this investigation are post-market devices, and are to be used as recommended by the manufacturers. For these reasons, there are no anticipated adverse device effects.

### 4.3 Risks associated with participation in the clinical investigation

The investigatory procedure and comparator procedure both carry risks typical to the standard of care of earmold impression procedures. When placing an object in the auditory canal, there is risk of discomfort to the participant. In addition, when equipment is placed too deep into the

SRF-371

Confidential and proprietary.

This document and its contents are confidential and proprietary to Sonova and shall not be reproduced or otherwise disclosed to anyone other than Sonova employees without written authorization from Sonova.

This printout is an uncontrolled copy. The original is stored in the Document Management System  
Template: TPL-368 [2]

Page 10/26

## Clinical Investigation Plan (CIP)

auditory canal, there is risk for damage or perforation of the tympanic membrane. There are risks of skin sensitivity to material of the devices inserted into the auditory canal, as well as risk for abrasions or irritation while placing these devices during the procedure.

### 4.4 Possible interactions with concomitant medical treatments as considered under the risk analysis

Exclusion criteria of this investigation removes the possibility of interactions with concomitant medical treatments.

### 4.5 Steps that will be taken to control or mitigate the risks

Researchers will be trained in accordance with the manufacturer's [REDACTED] recommendations specific to this product prior to data collection. The control condition (Silicone earmold impression procedure) is within the scope of practice of the research audiologists. The research audiologists are licensed by the state of Illinois and the procedures performed are within their scope of practice as defined by the licensing body.

Table 1: Summary of all controls taken to mitigate the risks of the product related residual risks.

Polarion Risk-ID –Auditory Canal Discomfort	
Risk Control	Researchers are trained in both procedures to limit this risk as much as possible. This training has been provided by the manufacturers of equipment. Performing this procedure complies with the scope of practice of their licensing body.
Polarion Risk-ID – Tympanic Membrane Perforation	
Risk Control	Researchers are trained in both procedures to limit this risk as much as possible. This training has been provided by the manufacturers of equipment. Performing this procedure complies with the scope of practice of their licensing body.
Polarion Risk-ID – Skin Sensitivity	
Risk Control	Researchers are trained in both procedures to perform them as safely and efficiently as possible. This allows the time of contact with equipment to be as limited as possible for participants, minimizing the risk of skin sensitivity occurrences.
Polarion Risk-ID – Skin Abrasions and Irritation	
Risk Control	Researchers are trained in both procedures to limit this risk as much as possible. This training has been provided by the manufacturers of equipment. Performing this procedure complies with the scope of practice of their licensing body.

### 4.6 Risk/benefit rationale and justification of the selection of clinical end-point(s).

The risks of this study are minimal as the procedures are within the scope of practice of the research audiologists, and manufacturer training recommendations are to be followed for the [REDACTED] 3D ear scanner. These limited risks are accompanied by the benefit of understanding whether or not the [REDACTED] 3D ear scanner will be beneficial to Audiological Care Clinics,

SRF-371

Confidential and proprietary.

This document and its contents are confidential and proprietary to Sonova and shall not be reproduced or otherwise disclosed to anyone other than Sonova employees without written authorization from Sonova.

This printout is an uncontrolled copy. The original is stored in the Document Management System  
Template: TPL-368 [2]

Page 11/26

## Clinical Investigation Plan (CIP)

particularly in terms of procedural timing and preferences for both patients and providers. To satisfy the primary objective, the entirety of the procedural workflow will be captured using a stop watch (mm:ss) for both conditions, in order to have a direct measure of the timing component of the investigation. To satisfy the secondary objective, subjective questionnaires will be administered to answer questions relevant to incorporating this product into clinics. Question domains will include, but are not limited to, patient comfort, patient's perceived level of involvement, researcher's ease of use, and both patient/provider confidence in the scan/impres- sion producing an appropriate earmold.

### 5 Objectives and hypotheses of the clinical investigation

#### 5.1 Purpose of the clinical investigation claims for clinical performance, effectiveness or safety of the investigational device that are to be verified

The purpose of this study is to better understand the value drivers behind the [REDACTED]. The study intends to find any significant difference in the time it takes to complete the workflow of the [REDACTED] 3D ear scanner impressions, compared to a traditional silicone earmold impression (EMI). A secondary purpose of this study is to identify preferences between the [REDACTED] and traditional methods, for both patients and providers. This information will allow us to find out whether this is a viable piece of equipment for Audiological Care clinics.

#### 5.2 Primary and Secondary Objectives

The Primary objective is to identify any significant differences in the time required for a provider to complete the workflow of an [REDACTED] 3D ear scanner, compared to traditional silicone earmold impression procedures. The secondary objective is to identify any significant preferences for both providers and patients.

#### 5.3 Scientific justification and clinical relevance for effect sizes, non-inferiority margins or equivalence limits

This is an exploratory trial, and as such, no specific effect size, non-inferiority margin, or equivalence limit is applicable.

#### 5.4 Safety Objectives

There are no risks or anticipated adverse device effects to be assessed for this investigation.

#### 5.5 Hypothesis

The study is exploratory in nature and will be used to further develop further hypotheses. The purpose of this study is to better understand the value drivers behind the [REDACTED]. The study intends to find any significant difference in the time it takes to complete the workflow of the [REDACTED] 3D ear scanner impressions, compared to a traditional silicone earmold impression (EMI). A secondary purpose of this study is to identify preferences between the [REDACTED] and traditional methods, for both patients and providers. This information will allow us to find out whether this is a viable piece of equipment for Audiological Care clinics.

## Clinical Investigation Plan (CIP)

### 6 Design of the clinical investigation

#### 6.1 General

##### 6.1.1 Design Type

This observational study will have two conditions ( [REDACTED] 3D ear scanner and a control condition - traditional silicone impression procedure) across a sample population of 30 human subjects. The order of conditions will be counterbalanced and blinding is not applicable.

##### 6.1.2 Measures for minimizing bias

Conditions will be counterbalanced across participants. In addition, three research audiologists will be involved in data collection in order to better represent the skill level of an average provider.

##### 6.1.3 Endpoints with rationale for their selection and measurement

To satisfy the primary objective, the entirety of the procedural workflow will be captured using a stop watch (mm:ss) for both conditions, in order to have a direct measure of the timing component of the investigation. To satisfy the secondary objective, subjective questionnaires will be administered to answer questions relevant to incorporating this product into clinics. Question domains will include, but are not limited to, patient comfort, patient's perceived level of involvement, researcher's ease of use, and both patient/provider confidence in the scan/impresion producing an appropriate earmold.

##### 6.1.4 Methods and timing for assessing, recording, and analyzing variables

To satisfy the primary objective, the entirety of the procedural workflow will be captured using a stop watch (mm:ss) for both conditions, in order to have a direct measure of the timing component of the investigation. To satisfy the secondary objective, subjective questionnaires will be administered to answer questions relevant to incorporating this product into clinics. Question domains will include, but are not limited to, patient comfort, patient's perceived level of involvement, researcher's ease of use, and both patient/provider confidence in the scan/impresion producing an appropriate earmold.

##### 6.1.5 Equipment to be used for assessing the clinical investigation variables and arrangements for monitoring maintenance and calibration.

To satisfy the primary objective, the entirety of the procedural workflow will be captured using a stop watch (mm:ss) for both conditions, in order to have a direct measure of the timing component of the investigation. To satisfy the secondary objective, subjective questionnaires will be administered to answer questions relevant to incorporating this product into clinics. Question domains will include, but are not limited to, patient comfort, patient's perceived level of involvement, researcher's ease of use, and both patient/provider confidence in the scan/impresion producing an appropriate earmold.

##### 6.1.6 Any procedures for the replacement of participants (not applicable to randomized clinical investigations)

In the event of attrition, a rolling recruitment approach may take place in order to maintain adequate power of the investigation.

##### 6.1.8 Definition of completion of the clinical investigation

The clinical investigation is considered complete when the study report has been reviewed and approved by the appropriate authorities.

SRF-371

Confidential and proprietary.

This document and its contents are confidential and proprietary to Sonova and shall not be reproduced or otherwise disclosed to anyone other than Sonova employees without written authorization from Sonova.

This printout is an uncontrolled copy. The original is stored in the Document Management System  
Template: TPL-368 [2]

Page 13/26

## Clinical Investigation Plan (CIP)

### 6.2 Investigational device(s) and comparator(s)

Description of the exposure to the investigational device(s)	For each subject, the investigational device (█████ 3D ear scanner) will have an exposure time of approximately 15 minutes, or the length of time it takes to complete a 3D ear scan in its entirety.
Description of the exposure to the comparator(s), if used.	For each subject, the comparator (silicone earmold impression procedure) will occur for approximately 15 minutes, or the length of time it takes to complete a traditional silicone earmold impression.
List of any other medical device to be used during the clinical investigation (if applicable)	N/A
Number of investigational devices to be used, and justification	1 – The investigational device can be reused and sanitized between subjects in accordance with the manufacturer recommendations.

### 6.3 Participants

Inclusion criteria for participant selection	Adult aged (18+ years) and any degree of hearing loss.
Exclusion criteria for participant selection	External auditory canal must be present and medically unremarkable to facilitate impressions. Participants with surgical ears or without external auditory canals must be excluded.
Criteria and procedures for participant withdrawal or lost to follow up	
During the consent process, participants agree to their involvement being completely voluntary and they may withdraw at any time. A participant is immediately withdrawn if requested to be removed from the investigation. In addition, in the event of an adverse event, the investigation will be paused until the event is reviewed and it is deemed safe to continue the investigation.
 
Attrition will be documented in an excel spreadsheet containing all collected data.
 
In the event of attrition, a rolling recruitment may take place in order to maintain adequate statistical power of the investigation.

Point of enrollment	Following the manufacturer recommended training protocol for the investigatory device for all researcher involved in data collection.
Point of randomization (if applicable).	N/A, conditions will be counterbalanced during enrollment.
Total expected duration of the clinical investigation	Approximately 1 month

SRF-371

Confidential and proprietary.

This document and its contents are confidential and proprietary to Sonova and shall not be reproduced or otherwise disclosed to anyone other than Sonova employees without written authorization from Sonova.

This printout is an uncontrolled copy. The original is stored in the Document Management System  
Template: TPL-368 [2]

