### 6.4 Procedures

#### 6.4.1 Investigation-related Procedure

Three researchers will be facilitating these appointments to limit variability of researcher skill across the two conditions. Researchers will familiarize themselves with the [REDACTED] equipment through independent practice prior to a training facilitated by [REDACTED] (occurring April 23rd) and the researchers will follow [REDACTED] training recommendations (perform scans on 20+ ears following in-person training) prior to data collection. Participants will be seen for one appointment. REUR/REUG, RECD, tympanometry, and reflex thresholds will be collected. The researcher will perform both traditional earmold impressions and 3D ear scans on both ears (conditions will be randomized and counterbalanced across participants). An additional researcher will use a stop watch to quantify the time (mm:ss) it takes for each condition, for both ears. After each procedure, participants and the clinician will also be asked to complete a questionnaire regarding each condition, focusing on their perception of comfort and level of involvement throughout the impression taking. In the event that a clinician feels as though a silicone impression needs to be remade, this will be recorded on the clinician questionnaire. Timing will be recorded for all attempts, but only the time recorded for the final impressions will be used in the data analysis. The resulting data will be compiled for all participants and analyzed using a T-test, to identify any significant differences in the time it takes to complete each method of earmold impressions, in addition to any differences in perceptual comfort.

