### 7.1 Determination of Sample Size

A priori sample size estimation was not performed for this investigation, as the investigation is exploratory and does not aim to confirm any effect with statistical significance and power.

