## Clinical Investigation Plan (CIP)

each methodology will be tested for normality using a Shapiro-Wilk test. If the data are normally distributed, additional analysis will proceed immediately. If data are not normally distributed, transformation(s) may be performed on the data, as appropriate, to achieve an approximately normal distribution of the response data for further analysis.

Data (raw or transformed, per above) will then be subjected to analysis via linear mixed effects modeling. The model will be constructed to regress (raw or transformed) procedure time on a dummy variable of methodology (fixed effect), with a random effect of audiologist. This model will allow the investigators to evaluate the relative difference in procedure time between the methodologies, while removing and separately evaluating the variance contributed by the audiologist undertaking the procedure.

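### The plan does not settle whether the order of the two methods is random, and it does not require order to be balanced within each audiologist's 10 participants

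*Combined protocol and SAP*

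**What the plan says.** Five places describe how order is set.

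- 1.3 (Measurements and procedures) and 6.4.1, in the same words: "conditions will be randomized and counterbalanced across participants".
- 6.3, Point of randomization: "N/A, conditions will be counterbalanced during enrollment".
- 6.1.1: "The order of conditions will be counterbalanced and blinding is not applicable".
- 6.1.2, where this is one of two listed bias controls: "Conditions will be counterbalanced across participants".

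The synopsis fixes the numbers: "N = 30 (10 participants per researcher). Both conditions will be measured for each participant". The primary model in 7.3.2 regresses procedure time on a "dummy variable of methodology (fixed effect), with a random effect of audiologist". It has no order term and no method-by-audiologist term. The dataset in 7.3.1 holds the audiologist, the participant ID, the method, and a running count of procedures per method and audiologist. First or second position within a participant is not listed. No section says how an order list is made, who holds it, or when an order is revealed.

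**The concern.** Read literally, 6.3 gives an order set by counterbalancing with no randomization, while 1.3 and 6.4.1 promise randomization. Site staff cannot tell which rule to follow, and a reader of the report could not tell which was followed.

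Order could matter here. Both procedures are done on the same ears in one appointment. In the timing details of 6.4.1, wax removal is listed before the silicone timer starts but is not listed for the scan. An ear done silicone-first may therefore be cleared before it is scanned, while an ear scanned first may not be. The documents give no size for any such effect.

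The analysis as written could not repair an uneven order. The model has no term for it, and the running count need not show which method came first: an audiologist's fourth participant can be number 4 for both methods.

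**Working it through.** **Inputs.** 30 participants, 3 audiologists, 10 each (1.3); 3 × 10 = 30, so the plan's own figures agree. Balance is stated across participants (1.3, 6.1.2, 6.4.1). Order effects are assumptions, because the documents give none.

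**1. Random list, 15/15 fixed over the 30 only.** Let a, b, c be the numbers of scan-first participants for the three audiologists, with a + b + c = 15:

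P(a, b, c) = C(10,a) · C(10,b) · C(10,c) / C(30,15), where C(30,15) = 155,117,520.

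- All three 5/5: 252³ / 155,117,520 = 16,003,008 / 155,117,520 = 10.3%.
- A given audiologist not 5/5: 1 − 252 × 184,756 / 155,117,520 = 70.0%. The same margin gives 24.5% for 7/3 or worse and 5.0% for 8/2 or worse.
- Worst split among the three, summed over all (a, b, c):

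| Worst split | Probability |
|---|---|
| 5/5 | 10.3% |
| 6/4 | 43.0% |
| 7/3 | 34.5% |
| 8/2 | 10.75% |
| 9/1 | 1.39% |
| 10/0 | 0.06% |

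Hence at least one audiologist at 7/3 or worse: 46.7%. At 8/2 or worse: 12.2%.

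**2. Non-random schemes that also meet the 6.3 wording.** Strict alternation gives 5/5 for every audiologist, whether participants come in rotation or in runs of 10, but the next order is always known. One order for the first 15 and the other for the last 15, with audiologists in runs of 10, gives 10/0, 5/5 and 0/10.

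**3. Effect on one audiologist's method difference.** Suppose the second procedure takes δ minutes longer or shorter. With k of 10 scan-first, the mean scan-minus-silicone difference shifts by δ × |2k − 10| / 10 in size: 0.4δ at 7/3, 0.6δ at 8/2, 1.0δ at 10/0.

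**4. Effect on the pooled difference.** Every analysed participant contributes both methods, so the pooled difference is the mean within-participant difference.

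- Common δ, 15/15 overall: the shifts cancel. For 7/3, 5/5, 3/7: (0.4 + 0 − 0.4) × δ / 3 = 0.
- Assumed δ of 2, 1 and 0 min by audiologist:
  - 7/3, 5/5, 3/7: (0.4 × 2 + 0 × 1 − 0.4 × 0) / 3 = 0.27 min.
  - 8/2, 5/5, 2/8: (0.6 × 2) / 3 = 0.40 min.
  - 10/0, 5/5, 0/10: (1.0 × 2) / 3 = 0.67 min.
- Exclusions under 7.4, which removes anyone missing either time: if three were lost, all from one order (assumed), 15/12 remains and the shift is (15 − 12) / 27 = 0.11 min per minute of common order effect.

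**5. After the fix.** With 5/5 within each audiologist, every term in step 3 is 0 for an additive order effect, even if δ differs by audiologist, until exclusions intervene.

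**The case against.** The 6.3 field is a template entry to be completed only where applicable, and the study is ticked as observational with one cohort. The entry may mean only that nobody is randomized to a group. That reading is fair, but it leaves the conflict in place: the same cell goes on to say how order is set and gives counterbalancing alone. If order is random, as 1.3 and 6.4.1 say, there is a point of randomization and it is missing.

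A stronger objection is that the plan estimates one pooled method effect. The only per-audiologist look is a possible visual one at learning curves (7.3.3), outside the statistical analysis. With 15/15 overall, a common additive order effect cancels however order falls within audiologists. This stands and limits the point. A reader might infer from the 47% figure that the primary comparison is biased; the documents do not support that.

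Three other inferences also go too far:

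- That order is both predictable and uneven. These come mostly from different schemes: alternation is predictable but even, and a random 15/15 list is often uneven but hard to predict. Only a scheme such as first-15/last-15 shows both.
- That staff could steer participants to an order and so bias the comparison. No section says who books participants, and each participant receives both methods, so selection does not put different people into the two methods.
- That order might be unbalanced overall by design. Every section that describes order says it is counterbalanced. Likewise, calling for balance across participants does not forbid 5/5 within audiologist; it only fails to require it.

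Finally, each method's introduction and first otoscopy come before its timer starts, so prior instruction should contribute little to the timed interval. The study is also exploratory, with no target effect size.

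**Conclusion.** The contradiction between 6.3 and 1.3/6.4.1 is real and lies within the current text. The absence of any within-audiologist balance rule is a genuine but modest weakness. Under a random list balanced only overall, some audiologist is at 7/3 or worse in 47% of lists and 8/2 or worse in 12%; these figures assume exactly 10 participants per audiologist and 15/15 overall.

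The pooled method difference is unbiased if the order effect is additive, on the scale analysed, and common to the audiologists. The remaining exposure is to any audiologist-level comparison, to the pooled difference if order effects differ by audiologist (0.27 to 0.67 min under the assumed effects of 2, 1 and 0 min), and to imbalance after 7.4 exclusions. This is a near-free improvement, not a threat to the primary result as planned.

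**What to change.** - State one rule, in the same words, in 1.3, 6.1.1, 6.1.2, 6.3 and 6.4.1.
- Use a pre-generated random order list for each audiologist, with 5 scan-first and 5 silicone-first. Reveal each participant's order at the visit after consent, and enter that as the point of randomization in 6.3.
- Add first/second position for each procedure to the 7.3.1 dataset, so that order can be included as a term in the 7.3.2 model. The list alone does not protect against exclusions under 7.4; the recorded position allows adjustment.

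The cost is one list, one data column and a few corrected sentences. One small trade-off: someone who tracks past orders would guess the next one correctly about 65% of the time with a 5/5 list of 10, against about 60% with a 15/15 list of 30 (simulated). As every participant has both methods, this matters little.
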